- (1) To determine if a relatively brief, focused intervention in reappraisal-by-distancing in bereaved spouses engages the targeted mechanisms. Hypotheses: Distancing training is expected to result in longitudinal reductions in self-reported negative affect, increases in RSA, and changes in neural activity in a priori ROI's above (i.e., reductions in amygdala activity, increases in DLPFC activity) that are greater than those for reinterpretation training.
- (2) To examine the impact of changes in the targeted mechanisms in changing health-relevant behavior. Hypotheses: Across time and participants, reductions in self-reported negative affect, increases in RSA, and changes in neural activity are expected to lead to reductions in depressive symptoms and grief rumination.
- (3) As an exploratory aim, to mechanistically relate intervention effects to behavior change as a function of changes in the targeted processes. Crucially, this aim will also include assessment of interactions with age and gender of the bereaved spouse and initial depression and grief severity.

Hypotheses: Distancing training will lead to reductions in grief rumination and depression that are mediated by changes in the targeted neurobiological and behavioral mechanisms.

Sample Size::

84 bereaved participants will be recruited (i.e., N=42 per each intervention cell) and randomly assigned to receive either Distancing Training or Reinterpretation Training.

Power Analyses:

Outcome: Self-reported negative affect

Sufficient power to assess self-reported negative affect outcomes will be achieved by recruiting 42 participants per training cell. This sample size estimate is based upon a power analysis using an approximate effect size ($d=.70$) previously reported for within and between-subjects behavioral analyses of longitudinal reappraisal training data¹. Power analyses using this approximate effect size indicate over 95% power ($\alpha=.05$) to detect within-group effects and 90% power ($\alpha=.05$) to detect between-group effects should be achieved with 36 participants per cell. Assuming all-cause attrition of 15% (which reflects a liberal upper bound given past participant attrition rates of approximately 10%), the proposed sample size should provide sufficient power to assess this outcome. Post-attrition, we expect to have analyzable complete data for approximately 36 participants per cell.

Outcome: Respiratory sinus arrhythmia (RSA)

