Data analysis will primarily use linear mixed models, incorporating fixed effects for Training Group (Distancing and Reinterpretation), Session (T1-T5), and Trial Type (for analyses involving the reappraisal task; Look Neutral, Look Negative, and Reappraise Negative), and their interactions, as well as a random effect consisting of an intercept for each participant. In each analysis, statistically significant and near-significant intercept variance reflects reliable differences between participants. We will examine additional models that incorporate and estimate random-effects slope variance across participants on the time effect (i.e., Session). Outcome variables will be repeated measures in self-reported negative affect, RSA⁵, and neural activity (Aim 1) and changes in health-relevant behavioral outcomes (e.g., depressive symptoms and grief rumination; Aims 2 and 3). In these analyses, gender, age, baseline depressive symptoms, expectedness of the loss, and current (non-excluded) medication use will be incorporated as covariates. Importantly, given that we anticipate enrolling an approximately equal number of men and women, we also anticipate having sufficient power to conduct exploratory analyses on the effect of gender (and age) on the hypothesized effects (all Aims). Further, Aim 3 will be investigated using multilevel mediation modeling^{6,7} involving training group assignment as the higher-level predictor (X); self-reported negative affect, RSA data, and neural activity as potential individual-level mediators (M); and health-relevant behavior (i.e., depressive symptoms and grief rumination) as individual-level outcome variables (Y). Note that this will model mediation as a time-dependent and experimental process, both of which help

to rule out alternative explanations. Other exploratory model paths will also be tested. Appropriate covariates indicated above will be incorporated in all mediation models.

Data and Safety Monitoring Plan:

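### The stated 90% between-group power is not the power of the Group x Session test that Aim 1 needs, and no primary contrast is named for that test

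*SAP*

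**What the plan says.** - **Aim.** SAP, Specific Aims, Aim 1 expects distancing to produce longitudinal changes in negative affect, RSA and neural activity "that are greater than those for reinterpretation training". This is directional, and it is about change over time by group. The SAP Introduction makes these mechanisms the primary endpoints.
- **Power.** SAP, Power Analyses repeats one statement for each outcome: d = .70, "over 95% power ($\alpha=.05$) to detect within-group effects" and "90% power ($\alpha=.05$) to detect between-group effects should be achieved with 36 participants per cell". It does not say whether the test is one- or two-sided. Nor does it say whether d refers to a level, a T1-T5 change or an interaction.
- **Model.** SAP, Data Analysis (All Outcomes) plans mixed models "incorporating fixed effects for Training Group (Distancing and Reinterpretation), Session (T1-T5), and Trial Type" (three levels, task analyses only), "and their interactions", with a random intercept. No term or contrast is named as the primary test. Session is not declared categorical or numeric. Additional models with a random slope on Session are mentioned.
- **Visits.** In the Protocol (Design; Self-report Questionnaires; RSA), negative affect and RSA are measured at all five sessions and fMRI at T1 and T5 only.

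**The concern.** The power statement and the hypothesis concern different tests. A two-group comparison has one degree of freedom. A Group x Session interaction with five session levels has four, and adding a three-level Trial Type gives eight. Extra degrees of freedom spread the test over patterns that nobody hypothesised. A significant omnibus interaction also has no direction: it could arise because distancing did worse, or because one middle session or the neutral trials differed. It does not by itself show greater reductions under distancing.

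Two things are at stake. The design may have less power for its primary aim than the SAP claims. And with Session coding, trial-type comparison and contrast all left open, the test can be settled after seeing where the groups differ.

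**Working it through.** **Inputs.** From the SAP: n = 36 per cell after attrition (42 x 0.85 = 35.7), d = .70, alpha .05. Assumed, because the documents do not say: d is standardised on the T5-T1 change, errors are compound-symmetric (random intercept only), and tests are two-sided unless noted.

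**1. Reproduce the SAP's figures.** Two-sample t test with 70 df, noncentrality d x sqrt(n/2) = 0.70 x sqrt(18) = 2.97.
- One-sided .05: 90.3%. This reproduces the stated 90%.
- Two-sided .05: 83.4%. This does not.
- Within-group paired t test, two-sided: 98.3%, consistent with the stated figure of over 95%.

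**2. Degrees of freedom if Session is a factor.**
- RSA: Group x Session (2-1)(5-1) = 4.
- Negative affect: three-way (2-1)(5-1)(3-1) = 8.
- fMRI: two sessions, so 1, or 2 with Trial Type.

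If Session is numeric, these become 1, 2, and 1 or 2.

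**3. Power of the 4-df test.** With residual SD s, the T5-T1 change has SD s x sqrt(2), so the final group difference is 0.70 x sqrt(2) x s and its square is 0.98 s². Let x be the share of that difference present at each session, and S the sum of (x - mean x)². Then lambda = (36/2) x 0.98 x S = 17.64 S, with 4 and 280 df. For the linear contrast c = (-2, -1, 0, 1, 2), lambda = 17.64 x (sum of c times x)² / 10, with 1 and 280 df.

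| Pattern of group difference, T1 to T5 | S | lambda, 4 df | 4-df power | Linear lambda | Linear power |
|---|---|---|---|---|---|
| Linear: 0, .25, .5, .75, 1 | 0.625 | 11.03 | 75.5% | 11.03 | 91.1% |
| Half at T2, rest at T5: 0, .5, .5, .5, 1 | 0.5 | 8.82 | 64.5% | 7.06 | 75.4% |
| Plateau from T3: 0, .5, 1, 1, 1 | 0.8 | 14.11 | 86.3% | 11.03 | 91.1% |
| Step at T2: 0, 1, 1, 1, 1 | 0.8 | 14.11 | 86.3% | 7.06 | 75.4% |
| Step at T5: 0, 0, 0, 0, 1 | 0.8 | 14.11 | 86.3% | 7.06 | 75.4% |
| Step at T3: 0, 0, 1, 1, 1 | 1.2 | 21.17 | 97.0% | 15.88 | 97.8% |

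The T5-T1 contrast has lambda 18 x 0.49 = 8.82 (1 and 70 df) and 83.4% power in every row, because d is placed on it.

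**4. Power of the 8-df test.** Assume a linear trend, an effect in Reappraise Negative only, and equal independent errors per trial type. Then lambda = 18 x 0.625 x (2/3) x delta²/s², with 8 and 980 df.
- d on the change in Reappraise Negative minus Look Negative: the SD of that double difference is 2s, so delta² = 1.96 s², lambda = 14.7 and power is 78.6%.
- d on the change in Reappraise Negative alone: delta² = 0.98 s², lambda = 7.35 and power is 43.5%.

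Under the second meaning of d, 1-df contrasts on the double difference fall too. T5 minus T1 has lambda 18 x 0.98/4 = 4.41 and 54.4% power (1 and 70 df). The linear trend has lambda 11.03/2 = 5.51 and about 65%.

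**5. fMRI.** With lambda 8.82, the 1-df test has 83.4% and a 2-df test 75.2%.

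**The case against.** A reader might infer that the SAP commits to 4-df and 8-df omnibus tests and so throws away power that a contrast would keep. The documents do not support that.

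- **The degrees of freedom are inferred.** The SAP gives none and states no omnibus decision rule. Session is listed beside two factors with named levels, which makes factor coding a natural reading, but the mention of a slope on Session is compatible with a numeric variable and hence 1 df. Any 1-df contrast can also be drawn from the same fitted model. This stands. It changes the point from a wrong test to an unspecified one.
- **Not every primary endpoint is affected.** fMRI has two sessions, so Group x Session already has 1 df. This stands.
- **A contrast does not always win.** For a step at T2 or T5 the 4-df test has 86.3% against 75.4% for a linear contrast, a loss of about 11 points, and it also slightly exceeds the 83.4% of T5 minus T1. For a step at T3 the omnibus test reaches 97%. The documents state no expected trajectory. This stands.
- **Part of the gap is sidedness.** Going from one- to two-sided takes the simple comparison from 90.3% to 83.4% before any degrees of freedom are added. This stands.
- **Compound symmetry is assumed.** Slope variance between participants would alter the error term for a linear contrast, so its figures above could be optimistic.

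What none of this answers is that the SAP gives no power for the interaction and no rule for which test decides Aim 1. Open coding makes that gap wider.

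**Conclusion.** The concern holds in limited form. The stated 90% matches a one-sided two-group comparison and is not secured for the Group x Session test that addresses Aim 1. If Session is a five-level factor, the 4-df test has about 64% to 86% power for gradual, early-plateau or single-step (T2 or T5) change; a step at T3 is the favourable exception. Under a linear trend, the 8-df test for negative affect has 79% or about 44%, depending on what d measures. The omnibus tests also cannot show direction on their own, whatever their power.

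The sizes rest on the meaning of d, the trajectory, compound symmetry and two-sided .05, none of which the SAP fixes. The mismatch between the power statement and the aim, and the absence of a named contrast, do not depend on those assumptions. This should be corrected; confidence is medium.

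**What to change.** In the SAP:

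1. State whether Session is categorical or numeric, and whether tests are one- or two-sided.
2. Name one 1-df Group x Session contrast per primary endpoint as the primary test. For RSA, use T5 minus T1 or the linear trend, chosen in advance. For negative affect, make the same choice in advance and apply it to Reappraise Negative minus Look Negative. For fMRI, use T5 minus T1 in each ROI.
3. Report the omnibus interactions as descriptive.
4. Say what d = .70 is standardised on, and replace the 90% with the power of the named contrast: about 83% two-sided for T5 minus T1 if d refers to that contrast.

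The cost is SAP wording only; recruitment, visits and treatment do not change. The stated power becomes less favourable. A linear contrast carries a real risk if change is a single step at T2 or T5 (about 11 points below the omnibus test), so the choice between it and T5 minus T1 should reflect the trajectory the investigators expect and be made before group differences are examined.

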## Methods:

**Reappraisal Intervention Procedure.** At sessions T1-T5, participants will complete a widely used image-based reappraisal task. In the task, participants view non-violent images from the IAPS with themes relevant to grief and loss in bereavement. Task images are distinct from training images but contain the same themes. Neutral images contain at least one person but are emotionally neutral. All images at every session will be unique, presented in a randomized order, and counterbalanced across sessions and negative trial types. In the task, images are preceded by a cue word (either “LOOK” or “DECREASE”). On LOOK trials, participants will be asked to look at the image to-follow and respond naturally to it. On DECREASE trials, participants will be instructed to apply the appropriate regulation strategy (i.e., either distancing or reinterpretation) to decrease their emotional response to the image. Participants trained in distancing will be asked to alter the way they think about a personal connection to situations by viewing the photos with a rational, impartial mindset or imaging the events happened a long time ago, whereas participants trained in reinterpretation will be asked to tell themselves a story about the photos that whatever is going on will soon be better than it is now or the pain the person is feeling will be easier to bear with time. The resulting three trial types are: LOOK paired with a neutral image (“Look Neutral”), LOOK paired with a negative image (“Look Negative”), and DECREASE paired with a negative image (“Reappraise Negative”). One hundred and eighty total negative and 90 total neutral images are used in the task, with 18 trials per trial type per session, distributed evenly among 3 task runs. Following the presentation of each image, participants will be asked to rate their negative affect on a scale of 1 (least negative) to 4 (most negative).

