**Self-report Questionnaires.** Negative affect ratings will be assessed at T1 through T5. Perceived stress will be assessed using the Perceived Stress Scale (PSS) at T1 through T5 and both follow-ups. Participants will complete additional self-report questionnaires at T1, T5, and both follow-ups measuring depressive symptoms using the Center for Epidemiologic Studies Scale (CES-D), intensity and nature of grief-related cognitive processes using the Utrecht Grief Rumination Scale (UGRS), and emotion regulation strategy use using the Emotion Regulation Questionnaire (ERQ).

**Functional Magnetic Resonance Imaging.** Participants will complete the picture task at sessions T1 and T5, while undergoing functional magnetic resonance imaging (fMRI) using a simultaneous multislice (SMS)-accelerated (3x) EPI acquisition protocol (63 axial slices; TR=1.2 s; TE=27 ms, 2-mm cubic voxels). Participants will be scanned in a 3.0T Siemens Vida MRI scanner at the Houston Methodist Research Institute outfitted with an MR-compatible LCD display and an MR-compatible 4-response button box. Participants will be screened for metal and other MR-contraindications before entering the scanner.

**RSA.** RSA will be continuously measured during sessions T1 through T5 non-invasively using a Corsense heart rate variability monitor by Elite HRV. RSA will be measured during a 5-minute resting epoch while seated.

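### The SAP does not say which mixed model decides Aim 1, and the model it states, with a participant intercept only, need not hold its 5% level if people differ in how they change

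*SAP*

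**What the plan says.** SAP, Data Analysis, All Outcomes, describes linear mixed models. For task outcomes the fixed part includes, besides group and session, "Trial Type (for analyses involving the reappraisal task; Look Neutral, Look Negative, and Reappraise Negative), and their interactions". Only one random term is specified for this model: "as well as a random effect consisting of an intercept for each participant". Slopes are mentioned later in the same paragraph: "We will examine additional models that incorporate and estimate random-effects slope variance across participants on the time effect (i.e., Session". On the data to be modelled it says "Outcome variables will be repeated measures in self-reported negative affect", and it lists RSA and neural activity as the other Aim 1 outcomes.

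SAP, Specific Aims, Aim 1, expects changes under distancing "that are greater than those for reinterpretation training". That is a between-group comparison of change.

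Protocol, Methods, gives the task "with 18 trials per trial type per session, distributed evenly among 3 task runs", which is 18 x 3 = 54 ratings per session. Scans take place at T1 and T5 only, and the picture task is done in the scanner.

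The SAP does not state:
- which model decides Aim 1, or how to choose between the two;
- whether the target is Group x Session or Group x Session x Trial Type;
- whether Session is linear or a factor;
- whether ratings enter singly or as cell means, and whether each scan contributes one contrast value or three trial-type values;
- a residual covariance structure.

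**The concern.** The person is randomised, so the error term for a group difference in change must contain the variation between people in change. A participant intercept removes differences in level only. Everything else within a person goes into one pooled residual, which has two opposite effects:

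- Variation in change is spread over all of a person's observations and is under-counted in the Group x Session standard error. With 54 ratings per session and about 36 people per arm this can be severe, and the test is then too liberal.
- Stable person-by-trial-type differences do not affect the balanced Group x Session contrast, but they inflate the pooled residual. The test is then too conservative.

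Aim 1 concerns the SAP's primary endpoints. Run as stated, the model could give a false advantage for distancing or miss a real one. With two models and no decisive one, the choice could also follow the results.

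**Working it through.** **The plan's own figure.** The SAP claims 90% power "to detect between-group effects should be achieved with 36 participants per cell" at d = .70 and alpha .05. A two-sample t-test with 36 per arm has noncentrality .70 x sqrt(36/2) = 2.97. This gives 90.3% power one-sided and 83.4% two-sided, so the figure reproduces only one-sided; the SAP does not state sidedness. The SAP gives no type I error for the mixed model beyond the nominal 5%.

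**Inputs.** From the documents: 36 per arm after attrition (SAP, Power Analyses), S = 5 sessions, C = 3 trial types, 18 ratings per cell. Assumed, because the documents give no variances: residual variance 0.5 per single rating or RSA value, hence 0.5/18 = .0278 for a cell mean; the SD of individual T1-T5 change; and the person-by-session (ps), person-by-trial-type (pc) and three-way (psc) variances. RSA is taken as one value per session (C = 1).

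**Formulas** (balanced data). K = 18 for single ratings, 1 for cell means and RSA. Sxx = 10 for T1-T5. Slope variance v = (change variance)/16.

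- Variance the intercept-only model uses: A = var_e + [(S-1)CK ps + (C-1)SK pc + (SC-1)K psc + Sxx CK v] / (SCK-1)
- True variance, linear Group x Session: var_e + CK ps + K psc + Sxx CK v
- True variance, three-way contrast (no slope differences by trial type): var_e + K psc
- r = true/A; type I error = 2[1 - Phi(1.96/sqrt(r))]; standard-error factor = sqrt(r)

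**Two examples, SD of change 0.2** (v = .04/16 = .0025).
- Single ratings, pc = 0: true = .5 + 10 x 54 x .0025 = 1.85; A = .5 + 1.35/269 = .505; r = 3.66; 31%.
- Cell means, pc = .20: true = .0278 + 10 x 3 x .0025 = .1028; A = .0278 + (2 + .075)/14 = .176; r = 0.58; 1%.

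**Linear Group x Session, intercept-only model**

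| Setting | r | Type I error |
|---|---|---|
| Single ratings, pc = 0, SD of change 0.1 / 0.2 / 0.3 | 1.67 / 3.66 / 6.92 | 13 / 31 / 46% |
| Cell means, pc = .20, same SDs | 0.27 / 0.58 / 1.08 | 0 / 1 / 6% |
| RSA, change variance 0.1 / 0.25 / 0.5 / 1.0 | 1.09 / 1.22 / 1.41 / 1.71 | 6 / 8 / 10 / 13% |

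**Group x Session x Trial Type, intercept-only model** (ps = .02, pc = .05, psc = 0 / .01 / .03)

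| Unit | r | Type I error |
|---|---|---|
| Single ratings | 0.91 / 1.22 / 1.80 | 4 / 8 / 14% |
| Cell means | 0.34 / 0.42 / 0.52 | 0.1 / 0.2 / 0.7% |

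**Where there is little or no effect.** RSA with Session as a five-level factor gave 4.9 / 5.3 / 5.6 / 6.1% in simulation over the same four change variances. For fMRI with one value per scan (S = 2, C = K = 1), A = var_e + ps/(2-1), which equals the true variance, so r = 1 and the test stays at about 5%.

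**Simulation check** (36 per arm). Linear RSA gave 5.9 / 7.4 / 9.9 / 13.8% in 10,000 runs. Task settings came within 2 points of the formulas in 2,500 runs each.

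**Do the alternatives work?**
- A t-test on each person's slope rejected 4.8-5.3% of the time in every setting of a separate simulation with 20,000 runs per setting.
- The planned random Session slope model gave 4.2-5.0% for RSA and 3.8-5.6% for single ratings, but 0-4.4% for cell means at pc = .20.
- For the three-way test on single ratings, a mixed model with person-by-session and person-by-trial-type effects but no three-way person term uses .5 + 8 x 18 psc/263 (263 = 269 - 4 - 2). At psc = .01 / .03 this is .505 / .516, against true .68 / 1.04, which gives 9 / 17%. That is worse than the intercept-only 8 / 14%. One contrast per participant gave about 5% at both settings.

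**The case against.** The strongest reply is that random slopes are already planned. The word introducing the analysis makes mixed models as a class primary; the SAP never labels the intercept-only version decisive. For linear Group x Session in RSA and single ratings the planned slope model holds close to 5%. That is correct, and a reader who inferred that the SAP overlooks random slopes would be wrong. What remains is that the slope models are additional, no rule makes them decisive, and a Session slope alone does not settle the task analysis.

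A second reply is that every size is assumed and that the largest rates need single-rating analysis, which the SAP does not state. This also stands: none of the percentages estimates this trial's error rate. Dependence on unstated choices is nevertheless part of the point.

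A third reply is that Session is listed as T1-T5 in the same form as the categorical factors. If it is a factor, RSA is barely affected. The mention of slope variance points to linear time, so the text supports either reading.

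It is tempting to infer that all Aim 1 tests are inflated. The documents do not support that: some settings are strongly conservative and two analyses are essentially unaffected. For fMRI with three trial-type values per scan the same two-way dependence applies, but there is no imaging basis in the documents for putting a size on it.

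**Conclusion.** The plan is wrong as written on this point, though the defect is narrower than a general inflation of Aim 1. The stated model lacks an adequate error term for a between-group comparison of change, and nothing makes the better model decisive. That part rests on the text alone.

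The statistical consequence is conditional on people differing in how they change. Its direction and size depend on the contrast, the coding of Session, the unit of analysis and variances that the documents do not give. Under the assumed variances the intercept-only test ranges from nearly 0% to 46% in the cases tabulated. The calculations take complete, balanced data with 36 per arm. The point should be fixed before analysis. Confidence in the gap is high; confidence in its size is limited.

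**What to change.** For each Aim 1 outcome, state the contrast, the coding of Session, the unit of analysis and one decisive model.

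- **RSA:** the participant random Session slope model already planned, or an unstructured covariance if Session is a factor.
- **Task ratings:** one contrast per participant (the linear trend over T1-T5 in the chosen trial-type contrast), compared between groups with the planned covariates. A mixed model is acceptable only if it has participant Session slopes that may differ by trial type, plus participant-by-session, participant-by-trial-type and, for single ratings, participant-by-session-by-trial-type effects.
- **fMRI:** each participant's T5 minus T1 change in the chosen trial-type contrast, compared between groups. With two scans this is the full change.

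Use the per-participant contrast if a mixed model does not converge, state how participants with missing sessions enter it, and report the intercept-only model as a sensitivity analysis.

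The cost is SAP wording and usually a larger Group x Session standard error. In the settings above it is about 1.04-1.3 times the intercept-only one for the RSA trend and 1.3 / 1.9 / 2.6 times for single ratings; for cell means at person-by-trial-type variance .20 it is 0.5-1.0 times. If d = .70 means the group difference in change divided by the between-person SD of change, which the SAP does not say, the per-participant contrast has 83% power two-sided with 36 per arm. Without a missing-session rule, that contrast also loses participants.

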### **Design:**

Recently-bereaved participants (i.e. approximately 6 months post-spousal loss) will be screened for eligibility, then randomly assigned to receive training in either distancing or reinterpretation, with five sessions occurring every 1-3 days, with longitudinal collection of affective, psychophysiological, and functional magnetic resonance imaging (fMRI) data. During the five sessions (T1-T5), participants will undergo cognitive emotion regulation training and an emotion regulation task in their respective training groups, complete questionnaires, and take a 5 minute RSA reading. Functional MRI scans will be acquired at T1 and T5. Follow-up questionnaire assessments of perceived stress, depressive symptoms and grief rumination will occur at one and two months post-intervention. We propose to recruit 84 participants in this study (i.e., 42 participants per intervention cell).

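### For the reappraisal-task outcomes, the planned random effects leave out participant-by-Trial-Type variation and unequal variance across trial types, so Group x Trial Type tests run too liberal and the Aim 1 change tests may err in either direction.

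*SAP*

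**What the plan says.** The SAP's Data Analysis section (All Outcomes) plans linear mixed models with fixed effects for Training Group, Session and "Trial Type (for analyses involving the reappraisal task; Look Neutral, Look Negative, and Reappraise Negative), and their interactions". The random part is given "as well as a random effect consisting of an intercept for each participant". One extension follows: "We will examine additional models that incorporate and estimate random-effects slope variance across participants on the time effect (i.e., Session"). No participant-by-Trial-Type term, trial-type-specific residual variance, other covariance structure or robust standard error is named. The later remark about further exploratory paths concerns the mediation models.

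The Protocol's Methods section describes the data. After each image participants "rate their negative affect on a scale of 1 (least negative) to 4 (most negative"). The task runs "with 18 trials per trial type per session, distributed evenly among 3 task runs". Of the neutral stimuli it says "Neutral images contain at least one person but are emotionally neutral". The Protocol's Design section adds "Functional MRI scans will be acquired at T1 and T5".

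Aim 1 (SAP, Specific Aims) predicts larger change over time under distancing than under reinterpretation. The SAP does not say which Trial Type contrast tests this, or whether the models are fitted to single trials or to cell means.

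**The concern.** Every participant contributes all three trial types at each task session, so Trial Type is a within-person factor. People may differ stably in how strongly negative images affect them and in how far the regulation instruction lowers their rating. A participant intercept shifts all three trial types together and cannot represent that; a Session slope cannot either. The variation falls into the pooled residual, where the model treats it as independent noise that averages out over sessions. In truth it does not average out, because the same personal deviation recurs at every session.

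Secondly, if ratings of neutral images cluster near the bottom of a four-point scale, they vary less than ratings of negative images. A single residual variance is then too small for contrasts between the two negative trial types and too large for contrasts against Look Neutral.

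Task negative affect and neural activity are among the primary endpoints (SAP, Introduction), so the standard errors at stake are those of the main mechanistic tests.

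**Working it through.** **The plan's own figure.** The SAP gives no standard error or type I error for the task models. The nearest figure is 90% between-group power with d = 0.70, alpha 0.05 and 36 per cell. With the normal approximation, d x sqrt(n/2) = 0.70 x sqrt(18) = 2.970. Power is Phi(2.970 - 1.645) = 90.7% one-sided and Phi(2.970 - 1.960) = 84.4% two-sided. The 90% is therefore reproduced one-sided; the SAP does not state sidedness. This is a plain two-group comparison and does not depend on the covariance structure, so it does not settle the present point.

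**Inputs.** From the documents: 36 analysable participants per arm, J = 5 sessions for ratings and J = 2 for fMRI, K = 3 trial types, 18 trials per cell. Assumed, because the documents give no values: participant-by-Trial-Type variance t2 at r = 0.25, 0.5 and 1 times the residual variance s2; and a Look Neutral residual variance v relative to the negative trial types. No participant differs in rate of change.

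**Step 1. Participant-by-type variance only, cell means.** The planned model pools all within-person variation:

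- pooled residual = s2 + t2 x J(K-1)/(JK-1), which is s2 + (10/14) t2 = s2 + 0.714 t2 for J = 5 and s2 + 0.8 t2 for J = 2;
- correct error term for Group x Trial Type = s2 + J t2;
- correct error term for change over sessions = s2, because stable deviations cancel in a difference between sessions.

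The SE ratio (model over true) is the square root of pooled over correct, and type I error is 2[1 - Phi(1.96 x ratio)].

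| J | r | Group x Trial Type: SE ratio, type I | Change (T5-T1): SE ratio, type I |
|---|---|---|---|
| 5 | 0.25 | sqrt(1.179/2.25) = 0.72, 15.6% | sqrt(1.179) = 1.09, 3.3% |
| 5 | 0.5 | sqrt(1.357/3.5) = 0.62, 22.2% | sqrt(1.357) = 1.16, 2.2% |
| 5 | 1 | sqrt(1.714/6) = 0.53, 29.5% | sqrt(1.714) = 1.31, 1.0% |
| 2 | 0.25 | sqrt(1.2/1.5) = 0.89, 8.0% | sqrt(1.2) = 1.10, 3.2% |
| 2 | 0.5 | sqrt(1.4/2) = 0.84, 10.1% | sqrt(1.4) = 1.18, 2.0% |
| 2 | 1 | sqrt(1.8/3) = 0.77, 12.9% | sqrt(1.8) = 1.34, 0.9% |

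A null simulation for J = 5 (4,000 data sets per setting) gave 15%, 21% and 29% for Group x Trial Type and 3.6%, 2.1% and 0.9% for Group x Session x Trial Type (Reappraise Negative minus Look Negative). With both extra variances at zero it gave 4.5% to 5.8%.

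**Step 2. Unequal variance only.** The pooled residual is (2 + v)/3 times that of the negative trial types.

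- Contrasts within the negative trial types: SE ratio sqrt((2+v)/3), which is 0.87 at v = 0.25 (type I 9.0%) and 0.84 at v = 0.11 (10.0%).
- Contrasts of a negative trial type with Look Neutral: SE ratio sqrt(2(2+v)/[3(1+v)]), which is 1.10 (3.2%) and 1.13 (2.7%).
- Group x Session averaged over trial types: unaffected, simulated at 4.9% to 5.0%.

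**Step 3. Both together, v = 0.25, J = 5, cell means.** The pooled residual is 0.75 + 0.714 r.

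- At r = 0.5 it is 1.107. Group x Trial Type: sqrt(1.107/3.5) = 0.56, 27%. Change within the negative trial types: sqrt(1.107) = 1.05, 3.9% (simulated 4.3% to 4.7%).
- At r = 1 it is 1.464. Group x Trial Type: 0.49, 33%. Change: 1.21, 1.8%.
- The two effects cancel for the change contrast when 0.75 + 0.714 r = 1, that is at r = 0.35.

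**Step 4. Single trials.** Each participant has 270 ratings, so the pooled residual is the trial variance plus (180/269) t2, against a correct Group x Trial Type term of trial variance plus 90 t2. If the cell-mean residual is pure trial noise, t2 is r/18 of the trial variance. For r = 0.25 to 1 with equal variances, Group x Trial Type rejects at 19% (ratio sqrt(1.009/2.25) = 0.67) to 42% (sqrt(1.037/6) = 0.42). The conservative effect on change contrasts almost vanishes, since sqrt(1.009) to sqrt(1.037) is 1.00 to 1.02. With v = 0.25 the pooled term is 0.759 to 0.787 and change within the negative trial types rejects at 8.8% to 8.2%.

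**Step 5. Does the Session slope repair it?** In 60 fits at r = 0.5, v = 0.25, adding a random Session slope left the Group x Trial Type SE ratio at 0.53 and type I error at about 30%.

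**Step 6. Participant-level contrasts.** In three of these scenarios, comparing each participant's contrast between groups held 4.3% to 5.0% for both Group x Trial Type and Group x Session x Trial Type.

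**The case against.** The strongest reply is that Aim 1 concerns change over sessions. Group x Trial Type pooled over T1 to T5 includes the baseline session, and no hypothesis is attached to it; it enters only because all interactions are fitted. A reader might take its inflated false-positive rate (12% to 60% in a simulation on the rating scale, over cell means and single trials) as the error rate of the Aim 1 test. The documents do not support that. In the same simulation, change within Reappraise Negative rejected at 0.3% to 1.6% on cell means and 6% to 7% on single trials. This part of the objection stands.

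Three other tempting readings also go too far.

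- That the error bars are wrong whatever the data look like. The documents give no mean, SD or floor rate for neutral images and no participant-by-type variance. If both features are absent, the planned model is correct.
- That the cell-mean change test is always conservative and loses power. With extra session-to-session noise of SD 0.2 to 0.4 in negative-image cells (assumed), it rejected at 7.5% to 8.9%, 4.9% to 6.8% and 1.8% to 6.2% for regulation-effect SDs of 0.15, 0.30 and 0.45. Any power-loss figure depends on the chosen variances.
- That ROI models suffer equally. They have two sessions and no four-point floor, and the ratios in Step 1 are milder.

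What does not stand is the inference that nothing need change. Aims 2 and 3 use the task measures as individual-level mediators and examine interactions with age, gender and initial severity, which presupposes that people differ on them. Zero participant-by-type variance is hard to assume alongside those aims.

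**Conclusion.** The omission is clear from the text; its size rests on assumed variances. Unless participant-by-Trial-Type variance and unequal variance across trial types are both negligible, the stated models give wrong standard errors for the task outcomes.

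- Group x Trial Type on five-session cell means: about 15% to 29% type I error for variance ratios of 0.25 to 1. For two-session fMRI, SE ratios of 0.89 to 0.77.
- Aim 1 change contrasts (Group x Session, Group x Session x Trial Type): from about 1%, through nominal, to about 6% to 10%, depending on which variance dominates and on whether single trials or cell means are modelled.
- Unaffected: RSA and the questionnaires, which have no Trial Type; and Group x Session averaged over trial types under unequal variance alone.

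The SAP should be changed before analysis. Because the large inflation falls on a term without a stated hypothesis and the effect on Aim 1 is of uncertain direction, this is a should-fix point, not a must-fix one.

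**What to change.** For task ratings and ROI activity, add a participant-by-Trial-Type random effect and a separate residual variance for each trial type, and keep the Session slope. Where these are thinly estimated, as with ROI cell means (two observations per participant per trial type), test Aim 1 with a participant-level contrast instead: for example, the T1-to-T5 change in Reappraise Negative minus Look Negative, compared between groups. State whether single trials or cell means are analysed, and name the contrast that tests Aim 1.

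Dropping Look Neutral and modelling only the two negative trial types is not a full substitute. It removes the possible floor, but still needs a participant-by-Trial-Type effect and still imposes one residual variance on Look Negative and Reappraise Negative.

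The cost is a few lines of SAP text and a slightly more complex model. A T1-to-T5 contrast uses only participants with both sessions and sets aside T2 to T4, which is a reason to keep the fuller mixed model for the ratings. No new data or participants are needed.
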